5.5 General Concomitant Medication and Supportive Care Guidelines

Because there is a potential for interaction of hydroxychloroquine with other concomitantly administered drugs through the cytochrome P450 system, the case report form must capture the concurrent use of all other drugs, over-the-counter medications, or alternative therapies. The Principal Investigator should be alerted if the patient is taking any agent known to affect or with the potential to affect selected CYP450 isoenzymes. Appendix B presents guidelines for identifying medications/substances that could potentially interact with the hydroxychloroquine. While not strictly prohibited, these medications should be avoided if at all possible. Hydroxychloroquine should also be used with caution in patients taking medicines which may cause adverse ocular or skin reactions.

5.6 Duration of Therapy

In the absence of treatment delays due to adverse event(s), treatment will continue for 14 days or until one of the following criteria applies:

- Disease progression,
- Intercurrent illness that prevents further administration of treatment,
- Unacceptable adverse event(s),
- Patient decides to withdraw from the study, or
- General or specific changes in the patient's condition render the patient unacceptable for further treatment in the judgment of the investigator.

5.7 Duration of Follow Up

Patients will be followed for 30 days after surgery or 30 days after completion of the last dose of hydroxychloroquine if no surgery is completed. Patients removed from study for unacceptable adverse event(s) will be followed until resolution or stabilization of the adverse event. Follow-up visit should be combined with subject standard of care post-operative visit. If that visit occurs prior to the 30 days post op, subject should be contacted 30 days or after completion of the last dose for adverse event assessment.

5.8 Criteria for Removal from Study

Patients will be removed from study when any of the criteria listed in Section 5.6 applies. The reason for study removal and the date the patient was removed must be documented in the Case Report Form.

6. DOSING DELAYS/DOSE MODIFICATIONS

The following dose levels will be considered:

| Dose Schedule | |
|------------------------|-----------------------------|
| Dose Level | Dose |
| | Hydroxychloroquine (mg/day) |
| Level -1 | 200 mg/day |
| STARTING DOSE: Level 1 | 400 mg/day |
| Level 2 | 800 mg/day |
| Level 3 | 1200 mg/day |

At the discretion of the PI and investigative team, additional dose levels may be considered, if the primary endpoint cannot adequately be determined by the dose levels listed above.

6.1 Study Specified Dose Modifications for Non-Hematologic Toxicities

| Nausea and/or Vomiting | Management/Next Dose for Hydroxychloroquine |
|--|--|
| ≤ Grade 1 | No change in dose |
| Grade 2 | Hold until ≤ Grade 1. Resume at same dose level. |
| Grade 3 or 4 | Hold* until < Grade 2. Resume at one dose level lower, if indicated.** |
| *Patients requiring a delay of >2 weeks should go off protocol therapy. | |
| **Patients requiring > two dose reductions should go off protocol therapy. | |
| Recommended management: antiemetics. | |

| Diarrhea | Management/Next Dose for Hydroxychloroquine |
|---|--|
| ≤ Grade 1 | No change in dose |
| Grade 2 | Hold until ≤ Grade 1. Resume at same dose level. |
| Grade 3 or 4 | Hold* until < Grade 2. Resume at one dose level lower, if indicated.** |
| *Patients requiring a delay of >2 weeks should go off protocol therapy. | |
| **Patients requiring > two dose reductions should go off protocol therapy. | |
| Recommended management: Loperamide antidiarrheal therapy Dosage schedule: 4 mg at first onset, followed by 2 mg with each loose motion until diarrhea-free for 12 hours (maximum dosage: 16 mg/24 hours) | |

| Diarrhea | Management/Next Dose for Hydroxychloroquine |
|---|--|
| Adjunct anti-diarrheal therapy is permitted and should be recorded when used. | |

| Visual Changes | Management/Next Dose for Hydroxychloroquine |
|--|--|
| ≤ Grade 1 | No change in dose |
| Grade 2 | Hold until ≤ Grade 1. Resume at same dose level. |
| Grade 3 or 4 | Hold* until < Grade 2. Resume at one dose level lower, if indicated.** |
| *Patients requiring a delay of >2 weeks should go off protocol therapy. **Patients requiring > two dose reductions should go off protocol therapy. | |
| The methods recommended for early diagnosis of "chloroquine retinopathy" consist of (1) fundoscopic examination of the macula for fine pigmentary disturbances or loss of the foveal reflex and (2) examination of the central visual field with a small red test object for pericentral or paracentral scotoma or determination of retinal thresholds to red. | |

| Pustular or Bullous Dermatitis | Management/Next Dose for Hydroxychloroquine |
|---|--|
| ≤ Grade 1 | No change in dose |
| Grade 2 | Hold until ≤ Grade 1. Resume at same dose level. |
| Grade 3 or 4 | Hold* until < Grade 2. Resume at one dose level lower, if indicated.** |
| *Patients requiring a delay of >2 weeks should go off protocol therapy. **Patients requiring > two dose reductions should go off protocol therapy. | |

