5.2 Agent Administration

Treatment will be administered on an outpatient basis. Reported adverse events and potential risks are described in Section 7. Appropriate dose modifications are described in Section 6. No investigational or commercial agents or therapies other than those described below may be administered with the intent to treat the patient's malignancy.

| Dose Schedule | |
|------------------------|------------------------------------|
| Dose Level | Dose |
| | Hydroxychloroquine (mg/day) |
| Level -1 | 200 mg/day |
| STARTING DOSE: Level 1 | 400 mg/day |
| Level 2 | 800 mg/day |
| Level 3 | 1200 mg/day |

Subjects will receive HCQ every day for 14 days, starting at least 14d before planned surgery and optimally ending day prior to surgery. Dosing can be extended 7 days if necessary due to unexpected delays. HCQ can be taken at any time of the day with meals. Tablets of HCQ are available in 200 mg strengths. HCQ will be administered in divided doses (twice a day) for doses above 200 mg/day to minimize nausea. The divided doses should be taken in the AM and at night with meals. Subjects will also be required to keep a medication diary and to present this at the end of the treatment. Should a subject have emesis and regurgitate the medication within 30 minutes of taking it, the dose may be repeated once, but if vomiting occurs longer than 30 minutes after ingestion, the dose should not be repeated. Subjects taking antacids, proton-pump inhibitors or H2-blockers should not take hydroxychloroquine within 4 hours of these medicines.

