7.3 Adverse Reactions

The following Council for International Organizations of Medical Sciences (CIOMS) frequency rating is used, when applicable: Very common $\geq 10\%$; Common ≥ 1 and $<10\%$; Uncommon ≥ 0.1 and $<1\%$; Rare ≥ 0.01 and $<0.1\%$; Very rare $<0.01\%$; Not known (frequency cannot be estimated from available data).

Blood and lymphatic system disorders

Not known: Bone marrow depression, anemia, aplastic anemia, agranulocytosis, leucopenia, thrombocytopenia.

Cardiac disorders

Not known: Cardiomyopathy, which may result in cardiac failure and in some cases a fatal outcome.

Chronic toxicity should be considered when conduction disorders (bundle branch block/atrioventricular heart block) as well as biventricular hypertrophy are found. Drug discontinuation may lead to recovery.

Ear and labyrinth disorders

Uncommon: Vertigo, tinnitus

Not known: Hearing loss including cases of irreversible hearing loss.

Eye disorders

Common: Blurring of vision due to a disturbance of accommodation which is dose dependent and reversible.

Uncommon: Maculopathies which may be irreversible.

Retinopathy with changes in pigmentation and visual field defects. In its early form it appears reversible upon discontinuation of the drug. If allowed to develop however, there may be a risk of progression even after treatment withdrawal.

Patients with retinal changes may be asymptomatic initially, or may have scotomatous vision with paracentral, pericentral ring types, temporal scotomas, abnormal color visions, reduction in visual acuity, night blindness, difficulty reading and skipping words. Corneal changes including edema and opacities. They are either symptomless or may cause disturbances such as halos around lights especially at night, blurring of vision or photophobia. They may be transient or are reversible upon discontinuation of therapy.

Not known: Macular degeneration which may be irreversible.

Gastrointestinal disorders

Very common: Abdominal pain, nausea

Common: Diarrhea, vomiting

These symptoms usually resolve immediately upon reducing the dose or upon stopping the treatment.

Hepatobiliary disorders

Uncommon: Abnormal liver function tests

Not known: Fulminant hepatic failure

Immune system disorders

Not known: Urticaria, angioedema, bronchospasm.

Metabolism and nutrition disorders

Common: Anorexia (usually resolves immediately upon reducing the dose or upon stopping the treatment).

Not known: hypoglycemia

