8.6 CONTRAINDICATIONS

Use of this drug is contraindicated (1) in the presence of retinal or visual field changes attributable to any 4-aminoquinoline compound, (2) in patients with known hypersensitivity to 4-aminoquinoline compounds, and (3) for long-term therapy in children.

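### The Visual Changes dose table in Section 6.1 lets hydroxychloroquine continue or restart with a Grade 1 drug-attributed retinal or visual field change, which Section 8.6 lists as a contraindication

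*Combined protocol and SAP*

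**What the plan says.** Section 6.1 handles eye events in one table, Visual Changes, with the same grade steps as nausea and diarrhea:

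- Grade 1 or below: "No change in dose".
- Grade 2: "Hold until ≤ Grade 1. Resume at same dose level". (The wording recurs in the other toxicity tables; the Visual Changes row is meant here.)
- Grade 3 or 4: hold until below Grade 2, then resume one level lower where indicated.
- Off therapy: only for a delay beyond two weeks or more than two dose reductions.

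A note inside the same table begins "The methods recommended for early diagnosis of 'chloroquine retinopathy' consist of" and goes on to fundoscopy and central field testing for scotoma. It attaches no action to a positive finding.

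Section 8.6 contraindicates HCQ "in the presence of retinal or visual field changes attributable to any 4-aminoquinoline compound". It gives no grade threshold.

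Section 7.3 says of retinopathy: "In its early form it appears reversible upon discontinuation of the drug". It continues: "If allowed to develop however, there may be a risk of progression even after treatment withdrawal".

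**The concern.** The table's note tells the investigator how to recognise retinopathy, but the rows then send that finding through the same steps as a gastrointestinal upset. No row requires the change to have resolved before HCQ is given again. Followed as written, Section 6.1 continues the drug in early retinal change, which is the stage at which Section 7.3 ties reversibility to stopping. What is at stake is possible lasting visual harm to a patient who is taking HCQ for a biomarker question before curative-intent surgery.

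Section 8.6 is a contraindication and not a competing stopping rule. The fault is that Section 6.1 does not carry it over.

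**Working it through.** The plan states no figure to reproduce. The check has three parts: the table against Section 8.6, a search for text that closes the gap, and the size.

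**1. Table against Section 8.6, for an HCQ-attributed retinal or visual field change**

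| Situation | Section 6.1 | Section 8.6 | Result |
|---|---|---|---|
| Present at Grade 1 | Full dose continues | Contraindicated | Conflict |
| Grade 2, hold period | Held | Contraindicated | Agree |
| Grade 2, improved to a persisting Grade 1 | Same dose resumes | Contraindicated | Conflict |
| Grade 3 or 4, hold period | Held | Contraindicated | Agree |
| Grade 3 or 4, improved to a persisting Grade 1 | One level lower, where indicated | Contraindicated | Conflict, softened by the qualifier |
| Fully resolved before restart | Resumes | Change no longer present | No direct conflict |

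Three conditions must coincide: the change is retinal or visual field, it is attributed to HCQ, and it is still present when dosing continues or restarts. Accommodation blurring and corneal effects fall outside the conflict.

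**2. Does other text close the gap?**

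- Section 5.4 (dose-limiting toxicity) counts attributed Grade 3 or 4 events. It does not reach Grade 1 or 2 and does not bar resumption in that patient.
- Sections 5.6 and 5.8 require removal once a listed criterion applies, including an unacceptable adverse event or a change that would "render the patient unacceptable for further treatment in the judgment of the investigator". Neither names retinal change.
- Section 6.2 closes by referring other Grade 3 or 4 toxicities to the principal investigator; lower grades are not covered.
- Section 7.2 asks only that unexplained visual symptoms raise suspicion of retinopathy.
- Appendix C asks patients to report eye problems. It gives no dosing rule.
- Of the three contraindications in 8.6, hypersensitivity is reflected in exclusion 3.2.5, and use in children is precluded by the age limit in 3.1.2. The retinal one has no counterpart in Section 3.

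No section requires HCQ to be stopped for an attributed retinal or field change.

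**3. Size**

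Inputs: n = 18 (Section 11.2); Section 7.3 lists maculopathy and retinopathy as Uncommon, 0.1% to under 1%; doses 200 to 1200 mg/day and a 14-day course (Section 5.2). The same section adds: "Dosing can be extended 7 days if necessary due to unexpected delays". A Day 7 visit is in the study calendar.

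Expected cases = n × p:
- 18 × 0.001 = 0.018
- 18 × 0.01 = 0.18

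Chance of at least one = 1 − (1 − p)^18:
- 1 − 0.999^18 = 0.0178, or 1.8%
- 1 − 0.99^18 = 0.1655, or 16.5%

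Because the rating stops short of 1%, the upper figures are limits.

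Further drug allowed if a Grade 1 change is found at Day 7 = remaining days × daily dose:

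| | 200 mg/day | 1200 mg/day |
|---|---|---|
| 14-day course, 7 days left | 1,400 mg | 8,400 mg |
| With extension, 14 days left | 2,800 mg | 16,800 mg |

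**The case against.** The strongest reply is that Section 8.6 is part of the same protocol and nothing says Section 6.1 overrides it. On this reading the note in the Visual Changes table helps the investigator identify retinopathy, after which 8.6 applies. Section 5.8 makes removal mandatory once an adverse event is unacceptable, and a change that contraindicates the drug would naturally qualify. What remains would be a missing cross-reference.

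This does not close the gap. Removal under 5.6 and 5.8 depends on someone judging the event unacceptable, and a table row that tells the investigator to leave the dose alone implies the opposite. The qualifier in the Grade 3 or 4 row does not extend to Grades 1 and 2, where the instruction is plain.

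Several points do stand:

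- The calendar schedules no eye examination, and Section 7.3 notes that retinal changes may be asymptomatic at first. A Grade 1 finding at Day 7 therefore depends on an unscheduled examination or a reported symptom.
- The 1.8% to 16.5% range covers any retinal event at that rating. It does not measure the smaller subset that meets the conflict.
- The 16.8 g figure combines the top dose, detection at Day 7 and a full extension.
- Permanent discontinuation goes a little beyond 8.6, which speaks of changes that are present. For a change that has resolved, stopping for good rests on the progression warning in 7.3 and on the short course.

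**Conclusion.** The concern holds. For an HCQ-attributed retinal or visual field change that is present at Grade 1, or persists at Grade 1 after a higher grade, Section 6.1 directs or permits dosing that Section 8.6 contraindicates. No other section resolves this.

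The practical size is small. At most about 0.18 retinal cases are expected in 18 patients on the protocol's own rating, and fewer would meet all three conditions. That rating is not specific to these doses or to a 14-day course, and Section 2.2 associates eye effects with chronic treatment, so the true figure may be lower. The conclusion assumes that the table covers retinal events, which its own note supports. It has no bearing on the dose-finding design or its operating characteristics. Rarity limits the priority, but the possible harm and the ease of correction mean the change should be made.

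**What to change.** Add one row to the Visual Changes table in Section 6.1: any retinal or visual field change judged attributable to HCQ, at any grade, means permanent discontinuation and removal from protocol therapy. Keep the graded hold and resume rule for all other visual symptoms, including accommodation blurring and corneal effects.

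The neutropenia table in Section 6.2 already has a row that takes the patient off protocol therapy, so the format is familiar. (That row overlaps with the Grade 3 or 4 resume row above it, so copy the format only.) Section 5.7 already provides follow-up until resolution or stabilization for patients removed for unacceptable adverse events. A bare cross-reference to 8.6 would remove the textual conflict, but it would leave open a restart after resolution.

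The cost is one table row and, rarely, a patient whose PAR-4 result reflects a shortened course. The row adds no eye examination, so it acts only on changes that are identified; early asymptomatic changes could still be missed.

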3.2 Exclusion Criteria

- 3.2.1 Patients with metastatic cancer and/or cancer that is not amenable to surgery (i.e. must be curative intent; locally advanced is acceptable).
- 3.2.2 Patients with significant malabsorption as determined by the treating physician.
- 3.2.3 Patients who are receiving any other investigational agents.
- 3.2.4 Patients with known brain metastases are excluded from this clinical trial because of their poor prognosis and because they often develop progressive neurologic dysfunction that would confound the evaluation of neurologic and other adverse events. Patients with primary brain tumors amenable to surgery are allowed on this protocol.
- 3.2.5 History of allergic reactions attributed to compounds of similar chemical or biologic composition to hydroxychloroquine.
- 3.2.6 Caution should be taken with the use of hydroxychloroquine and any drugs known to interact with it (Appendix C). Because the lists of these agents are constantly changing, it is important to regularly consult a frequently-updated list such as <http://medicine.iupui.edu/clinpharm/ddis/table.aspx>; medical reference texts such as the Physicians' Desk Reference may also provide this information. As part of the enrollment/informed consent procedures, the patient will be counseled on the risk of interactions with other agents, and what to do if new medications need to be prescribed or if the patient is considering a new over-the-counter medicine or herbal product. Appendix C contains a list of known drug interactions with hydroxychloroquine.
- 3.2.7 Uncontrolled intercurrent illness including, but not limited to, ongoing or active infection, symptomatic congestive heart failure, unstable angina pectoris, cardiac arrhythmia, or psychiatric illness/social situations that would limit compliance with study requirements.

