6.2 Study Specified Dose Modifications for Hematologic Toxicities

| Neutropenia | Management/Next Dose for Hydroxychloroquine |
|---|--|
| ≤ Grade 1 | No change in dose |
| Grade 2 | Hold until ≤ Grade 1. Resume at same dose level. |
| Grade 3 or 4 | Hold* until < Grade 2. Resume at one dose level lower, if indicated.** |
| Grade 4 | Off protocol therapy |
| *Patients requiring a delay of >2 weeks should go off protocol therapy. **Patients requiring > two dose reductions should go off protocol therapy. | |

| Thrombocytopenia | Management/Next Dose for Hydroxychloroquine |
|---|--|
| ≤ Grade 1 | No change in dose |
| Grade 2 | Hold until ≤ Grade 1. Resume at same dose level. |
| Grade 3 or 4 | Hold* until < Grade 2. Resume at one dose level lower, if indicated.** |
| *Patients requiring a delay of >2 weeks should go off protocol therapy. **Patients requiring > two dose reductions should go off protocol therapy. | |

All other grade 3 or 4 toxicities should be discussed with the PI.

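### The skin-eruption table in 6.1 gives restart rules for hydroxychloroquine with no exception for drug hypersensitivity or a severe cutaneous drug reaction, and its Grade 2 row conflicts with 8.6(2) when hypersensitivity is diagnosed

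*Combined protocol and SAP*

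**What the plan says.** Section 5.2 sends the reader to Section 6 for dose modifications. In 6.1, the table headed "Pustular or Bullous Dermatitis" has three rows. At Grade 1 or lower nothing changes. After a Grade 2 eruption the instruction is "Hold until ≤ Grade 1. Resume at same dose level", which means a return to full dose. For an eruption of Grade 3 or 4 the instruction becomes "Hold* until < Grade 2. Resume at one dose level lower, if indicated". Two footnotes follow. One concerns delay: "Patients requiring a delay of >2 weeks should go off protocol therapy". The other concerns repeated reductions: "Patients requiring > two dose reductions should go off protocol therapy". Their marks (* and **) appear on the Grade 3 or 4 row only. The nausea, diarrhea and visual-change tables use the same wording.

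Elsewhere in the protocol:

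- 7.3 lists bullous eruptions, toxic epidermal necrolysis, Stevens-Johnson syndrome, DRESS and AGEP among the skin reactions to hydroxychloroquine (HCQ), with frequency not known. For AGEP it links a good outcome to stopping the drug.
- 8.6(2) contraindicates HCQ "in patients with known hypersensitivity to 4-aminoquinoline compounds".
- 3.2.5 excludes patients with "History of allergic reactions attributed to compounds of similar chemical or biologic composition to hydroxychloroquine".
- 5.6 ends treatment for an unacceptable adverse event or on the investigator's judgment. 5.8 then requires removal from study, and 5.7 requires follow-up of the event.

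**The concern.** Hold-and-resume is ordinary tolerability management for nausea, diarrhea or a falling count. A pustular or bullous eruption can be different in kind, because it may be an allergic or severe cutaneous reaction to the drug itself. In that case the question is whether the patient should receive the drug again at all. The table covers only when to restart and at what dose.

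A patient who had reacted allergically to a similar compound before entry would be excluded by 3.2.5. If the reaction first appears on study and is Grade 2, the table says to restart at full dose on recovery. The patients are awaiting curative-intent surgery (3.2.1), and the objectives in Section 1 concern PAR-4, toxicity and pharmacokinetics, not benefit to the patient. An avoidable re-exposure would therefore have nothing in the plan to set against it.

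**Working it through.** No arithmetic settles this point, so the check sets the sections side by side.

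**1. Grade 2.** The row tells staff to resume and adds no qualifier. It does not ask about cause, although 7.4 supplies a five-level attribution scale that could be used. Neither footnote is marked on this row.

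**2. Grade 3 or 4.** The closing words of this row leave room not to restart. They name no ground for that decision, so the row is softer than the Grade 2 row but has no stated exception either.

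**3. Footnotes.** One depends on the length of the delay and the other on the number of reductions. Neither depends on cause. The delay footnote also has little room to act. A delay of more than 14 days means at least 15 missed days. If the first missed dose is on calendar day d, dosing resumes no earlier than day d + 15.

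- d = 2 gives day 17, after the planned 14-day course has ended.
- d = 6 gives day 21, the last day if the 7-day extension in 5.2 is used (14 + 7 = 21).
- d = 7 gives day 22, beyond any permitted dosing.

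So the delay footnote cannot prevent a restart within the 14-day course, and within the extended course it could matter only for a hold starting by day 6.

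**4. Against 8.6(2).** Suppose the investigator concludes that a Grade 2 eruption is HCQ hypersensitivity. The patient then has known hypersensitivity and the drug is contraindicated. The Grade 2 row still says to resume. The two instructions cannot both be followed.

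**5. Other controls at Grade 2.** The PI-discussion sentence at the end of 6.2 covers only other Grade 3 or 4 toxicities. Section 7.5.3 requires no expedited report for expected Grade 2 or 3 events, even when related. The DSMC reviews all adverse events (4.4), but on a schedule that the protocol does not give (10.1.2). None of these was written as a restart control, so none can be relied on to act before one.

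**6. Whether Section 6 can state a stop.** It can. The neutropenia table in 6.2 has a Grade 4 row reading "Off protocol therapy".

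**The case against.** The strongest reply is that the protocol already resolves the case. The conflict arises only after an investigator has diagnosed hypersensitivity. At that moment 8.6(2) contraindicates the drug, 5.6 permits a stop, and 5.8 makes removal mandatory once a 5.6 criterion applies. The harm needs someone to follow the table and ignore the diagnosis. Much of this stands, and it is why the point is minor. It does not dispose of the point: 5.6 is general and discretionary, it does not mention hypersensitivity, and the table refers to neither 5.6 nor 8.6. The explicit instruction in the place where staff are sent remains to resume.

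Some stronger readings are tempting but unsupported:

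- *Every pustular or bullous eruption triggers 8.6(2).* The documents do not say so. Section 7.3 lists these eruptions under skin disorders and puts urticaria, angioedema and bronchospasm separately under immune disorders. The conflict depends on the investigator's judgment.
- *Section 5.4 binds staff to the Grade 2 row.* Its referral to Section 6 concerns dose-limiting toxicities, and a Grade 2 eruption is not one.
- *A probability of harm in 18 patients can be given.* Section 7.3 defines not known as a frequency that available data cannot estimate. Any rate would be invented, and a restart also needs recovery with dosing days left before surgery.
- *All restarts after a drug-related eruption should be barred.* Stepping down a dose level makes sense mainly for drug-related events, so that rule would largely empty the sponsor's table. Where to set such a threshold is debatable.

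**Conclusion.** The point holds in a narrow form. The 6.1 table states restart rules with no exception for HCQ hypersensitivity or a severe cutaneous drug reaction. Its unqualified Grade 2 instruction contradicts 8.6(2) once the eruption is judged to be hypersensitivity. The Grade 3 or 4 row has the same omission, softened by the discretion in its wording.

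Severity is minor. The frequency is unknown, the course is short, and other sections allow a stop. The conclusion rests on two readings: that staff use the table as the working rule for this event, as 5.2 directs, and that a reaction diagnosed on study counts as known hypersensitivity under 8.6(2). A reader might infer that the protocol orders contraindicated treatment as a matter of course, or that the choice of dose is affected. The documents support neither inference.

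**What to change.** Add one note under the table:

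*Do not resume HCQ if the eruption is judged an HCQ hypersensitivity reaction (8.6) or if SJS/TEN, DRESS or AGEP is suspected; the patient goes off protocol therapy and is followed per 5.7. Discuss any other Grade 2 or higher eruption at least possibly related to HCQ with the PI before restart.*

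This keeps the sponsor's hold-and-resume rule for all other eruptions and uses the attribution scale already in 7.4. It adds no visits, procedures or patients. The cost is that an occasional patient stops the 14-day course early and is removed under 5.8. One such patient is 1 of 3 in a cohort and 1 of 18 overall, and the protocol gives no replacement rule.
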